5.7 Strategies For there reduction of the bias

To the end Of reduce the possible bias in the assessment from the healing from the wound from part of the experimentedor he comes introduced a further analyses For to determine The degree Of healing from the wound: morphometric analysis of the wound. A digital photograph of the lesion will be taken at each visit for a total Of 4 Images (baseline, visit 1-3). The photos they will be taken following the recommendations of the Work Of Checked et to the. "Lieutenant top tips: wound photo documentation"¹³ For obtain Images standardized. The analysis morphometric from the wound consists in the assessment from the healing from the wound through there measurement from the wound performed with a software specific. Such measurement it is objective and not subject to the experimenter's interpretation. The size of the lesion will vary calculated at baseline and visits 1-3, healing will be expressed as a percentage of baseline.

Documento Studio WOUND-H Valutazione prestazioni e sicurezza [acido ialuronico lineare per il trattamento delle ferite]	Codice NA-01-23		
v. 2 del 26 giugno, 2023			

6 Collection Data

6.1 Consent informed

After have received the instructions complete concerning there nature, The meaning, the impact And the risks Of this clinical investigation, the patient must give written consent to participate in the study. During education patients must be informed that they can withdraw their consent, without provide reasons, at any time without their further medical care being affected in any way. In addition to the comprehensive instructions given to patients by the investigator, patients receive Also a form information written For The patient in a language understandable, That explains there nature And the scope of the study And The his progress. THE patients they must accept there possibility That the data concerning at the study are transmitted to the competent authorities. Patients must be informed in detail of the They obligations in relation to insurance For Not to compromise there coverage insurance

6.2 Information clinics

The clinical/medical history of the patients will be obtained at the screening visit (Visit 0) with particulars Attention to as follows:

- Acquisition of information clinics on state general of the patient included pathologies previousor current, including The conditions Of interest, habits regard to smoking.
- Pharmacotherapy, use chronic Of any drug (prescribed And to the bench, included The supplementsfood);
- History Of allergies or reactions idiosyncratic to the drugs;

6.3 Examination Physicist

A complete physical examination will be conducted at visit 1 and will include measurements of height, weight. The weight will be measured on a standard calibrated scale. Subjects must be dressed in indoor clothing light without shoes. Weight will be documented in kilograms to the nearest tenth of a kilogram. For the measurements of the height, the subjects they must to be measure yourself without shoes. The height will be documented to the tenth Of centimeter more Neighbor. The exam physicist will be executed from a doctor authorized. Full details of the physical examination will be recorded in the source documents at the implementing siteof the study.

Documento Studio WOUND-H Valutazione prestazioni e sicurezza [acido ialuronico lineare per il trattamento delle ferite]	Codice NA-01-23		
v. 2 del 26 giugno, 2023			

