5.1 Scheme of the protocol clinical

Visit 0 Screening: collection information clinics on the patient, inclusion

Visit 1 Baselines: assessment clinic, Clinical Healing scores, photography from the wound, start Treatment.

Visit 2 Follow up 1 (7 days Of treatment): assessment clinic, Clinical Healing scores, assessment a che to the dressing change, assessment reactions adverse, photography from the wound.

Visit 3 Follow up 2 (at the desaturation): assessment clinic, Clinical Healing scores, assessment a che to the dressing change, assessment reactions adverse, photography from the wound.

Visit 4 (30 days Of treatment): assessment clinic, Clinical Healing scores, assessment a che to the exchange dressing, determination healing wound, photography from the wound And collection events adverse.

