The sample size was calculated based on estimates of possible improvement in the Clinical Healing score at the desaturation (18-20 days) respect at the baseline using the information obtained from the literature^{5,6,8,10,11,14}. Sample size estimates were calculate in terms Of a variable Of answer continues hypothesizing a distribution Not normal, The change of the Clinical Healing score at the desaturation with a effect size (dz) Of 0.5 And considering 80% power. With these assumptions, the minimum required sample size is 53 subjects per treatment group. Therefore, considering a dropout rate of 5%, it is necessary the recruitment of 112 subjects.

Documento Studio WOUND-H Valutazione prestazioni e sicurezza [acido ialuronico lineare per il trattamento delle ferite]	Codice NA-01-23		
v. 2 del 26 giugno, 2023			

15 Analyses statistics

the primary endpoint is the improvement in the Clinical Healing score at visit 3 compared to baseline (visit 1). Assuming that the average change in Clinical Healing score for each treatment is Like this represented: Prog = result of the Clinical Healing score at the visit 2; BAS = result of the Clinical Healing score at baseline, the null hypothesis is represented by Prog = BAS and the alternative one by Prog \neq BAS. Statistical tests (Mann-Whitney test) will be conducted at a significance level of 0.05 per show improvement in Clinical Healing score at visit 3. Secondary endpoints will be analyzed as follows: Clinical Healing score at visits 2 and 4 - Mann-Whitney tests conducted at significance level equal to 0.05; The pain perceived by the patient when changing the dressing visits 2, 3 and 4 - Mann-Whitney tests conducted at the significance level of 0.05; The percentage of patients with a completely healed wound at visit 4 - two proportion z tests conducted at the level of significance even to 0.05.

16 Timings

The study involves the recruitment of 112 patients, it is estimated that this number of patients will be recruited a time of approximately 8 months. Considering that the time required to complete the follow-up for each patient is 30 days the overall duration of the study is estimated from the first date visit of the first patient will be Of 10 months. There relation the final will be provided After 3 months from the conclusionof the study.

17 Publication of the results

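### The primary endpoint gets an unadjusted Mann-Whitney test although the visit 1 score, smoking and body size are recorded before treatment; a pre-specified adjusted rank analysis could add power without more patients

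*Combined protocol and SAP*

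**What the plan says.** Section 15 states that "the primary endpoint is the improvement in the Clinical Healing score at visit 3 compared to baseline (visit 1". The test is given as "Statistical tests (Mann-Whitney test) will be conducted at a significance level of 0.05". The other score and pain comparisons are also Mann-Whitney tests, and complete healing gets a two-proportion z test. Section 15 names no covariate, stratum or adjusted model, and section 5.5 describes 1:1 blocks without a stratification factor. One line of section 15 defines the follow-up score at visit 2. I follow the endpoint and test sentences, which both say visit 3, and read the Mann-Whitney test as a comparison between arms.

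Three sets of data exist before treatment can affect them:

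- The visit 1 score. The section 5.1 schedule reads "Visit 1 Baselines: assessment clinic, Clinical Healing scores, photography from the wound, start Treatment".
- Smoking, in the screening history of section 6.2: "including The conditions Of interest, habits regard to smoking".
- Height and weight, in section 6.3: "A complete physical examination will be conducted at visit 1 and will include measurements of height, weight".

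Section 14 sizes the trial "with a effect size (dz) Of 0.5 And considering 80% power" and concludes that "the minimum required sample size is 53 subjects per treatment group". It makes no allowance for covariates.

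**The concern.** An unadjusted comparison leaves in the error term any variation in outcome that baseline data could explain. The trial uses the visit 1 score only by subtracting it. Patients who start with a low score have more room to improve, so change usually still depends on the starting score. A two-group rank test cannot use that dependence, nor any information in smoking or body mass.

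What is at stake is power. Adjustment fixed in advance keeps the false-positive rate and needs no extra patients. Covariates chosen after the data are seen would not be credible, so the choice belongs in section 15 now.

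**Working it through.** **Inputs from the documents:** 53 per group, effect size 0.5, 80% power and 5% dropout (section 14); Mann-Whitney test at 0.05, with the alternative written as not equal (section 15). **Assumed, because the documents give no figure:** the correlation ρ between visit 1 and visit 3 scores (0.3, 0.5, 0.7), and the share R² that smoking and body mass index explain beyond the visit 1 score (0 to 20%).

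**1. The plan's own figure.** A one-sided two-sample t-test with effect 0.5 and 80% power needs 50.15 per group. Dividing by the Mann-Whitney efficiency 3/π gives 50.15 × π/3 = 52.5, so 53. Dropout: 106 / 0.95 = 111.6, so 112. Both match. The two-sided version gives 63.77 × π/3 = 66.8, so 67. With 53 per group, two-sided power is 70.2%. The calculations below are two-sided, as section 15 writes the alternative.

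**2. What the visit 1 score adds, in closed form.** Assume equal spread at both visits, scaled to 1.

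- Variance of change: 2(1 − ρ).
- Residual variance after adjusting for the visit 1 score: 1 − ρ².
- Ratio: (1 + ρ)/2, which is 0.65, 0.75 and 0.85 for ρ = 0.3, 0.5 and 0.7.

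The effect of 0.5 SD of change becomes 0.5/√ratio = 0.620, 0.577 and 0.542. The effective n is 53 × 3/π = 50.6 per group. Power is about Φ(d × √(50.6/2) − 1.98), where √(50.6/2) = 5.03:

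- unadjusted: Φ(2.515 − 1.984) = 70%
- ρ = 0.3: Φ(3.120 − 1.984) = 87%
- ρ = 0.5: Φ(2.904 − 1.984) = 82%
- ρ = 0.7: Φ(2.728 − 1.984) = 77%

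The gains are about 17, 12 and 7 points. This treats the score as continuous.

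**3. Simulation on a 5-level score.** 53 per arm, two-sided 0.05, effect 0.5 SD of the latent change:

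| ρ | Mann-Whitney on change | Rank regression with visit 1 score | Gain |
|---|---|---|---|
| 0.3 | 63% | 82% | 19 |
| 0.5 | 62% | 75% | 13 |
| 0.7 | 57% | 66% | 9 |

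A second set of runs of the change-score model gave 47% against 67% at ρ = 0.3 (gain 20) and 76% against 85% at ρ = 0.7 (gain 9), with false-positive rates near 5%. The absolute power therefore depends on the set-up, while the gain stays at about 9 to 20 points.

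**4. What smoking and body mass index add to that model.**

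| R² beyond the visit 1 score | Change in power |
|---|---|
| 0 | loss of at most about 1 point |
| 10% | gain of about 2 points |
| 20% | gain of 3 to 6 points |

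**5. Where the visit 1 gain vanishes.** If the visit 1 SD is k times the visit 3 SD, the share of the variance of change explained by the visit 1 score is (k − ρ)² / (1 + k² − 2ρk). This is zero when k = ρ, for example when starting scores vary little. The documents do not report the spread at visit 1.

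**The case against.** The strongest reply is that nothing is broken. Computer-generated 1:1 randomisation makes the Mann-Whitney test valid, and its error rate already allows for chance imbalance between arms. On its one-sided inputs the plan has the 80% power it claims. Preferring a regression to a valid test is a choice. All of that stands, and it is why this is not listed as an error.

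A reader might infer that smoking and body mass are known to drive healing here, so that precision is certainly being lost. The documents do not support that. Section 6.2 lists smoking as part of history-taking, section 6.3 describes a routine examination, and neither calls these variables prognostic or gives an R². With weak predictors the extra terms cost slightly more than they return.

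A reader might also want days since surgery in the model, or suppose that the case report form omits height and weight. The documents do not list the first as a study variable. On the second, section 6.3 says only that full examination details go into source documents.

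The reply that baseline is already used, because the endpoint is a change, does not stand. Steps 2 and 3 show that subtraction captures only part of what the visit 1 score offers, unless k is close to ρ.

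**Conclusion.** The point holds as an optional, low-cost efficiency improvement. Section 15 pre-specifies no covariate adjustment although suitable baseline data are collected.

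The main gain is from the visit 1 score: about 9 to 20 points of power in simulation (7 to 17 in closed form). This rests on assumed correlations of 0.7 to 0.3 and on similar spread at both visits, and it could be nil if visit 1 scores hardly vary. For smoking and body mass index the effect lies between a loss of about 1 point and a gain of 3 to 6 points over the assumed R² range of 0 to 20%, so no firm benefit can be claimed.

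A reader might go further and take the unadjusted test to be biased, or chance imbalance to invalidate it. Randomisation rules out both. The gap between a sample size that reproduces only one-sided and a two-sided alternative is a separate matter. It makes spare power more useful, but adjustment does not resolve it.

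**What to change.** In section 15, state before any outcome data are seen that the primary comparison is a rank regression of the change in Clinical Healing score (visit 1 to visit 3) on treatment arm, with these fixed covariates:

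- visit 1 score
- current smoking (yes/no)
- body mass index from the section 6.3 height and weight

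Keep the plain Mann-Whitney test as a sensitivity analysis. State a simple imputation rule for a missing covariate value, so that no randomised patient is lost from the model.

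The cost is a few lines of text, one regression model and three degrees of freedom. No new measurement or extra patient is needed. If the sponsor wants the smallest change, adding the visit 1 score alone captures most of the expected gain.

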6.4 Registration of the data

The use of black ink is required for completed subject questionnaires. If they are necessary changes, subjects need to be asked to make changes by drawing a line on the unwanted response, and then recording the desired response. Once a subject returns the questionnaire, it will not be allowed any edit.

6.5 Collection And storage of the questionnaires

Upon completion of the questionnaires, the investigator will retrieve the questionnaires and check that the section of the header (Number object, Date Of visit, etc.) is was completed. The experimenter (or designated qualified member of their staff) will use the questionnaires completed by the individual to insert the data sign in in the section appropriate eCFR. There version original of the questionnaires filled out will remain with the documents originals of the subject. A survey compiled Not needs to to be returned to the subject when they will be returned to the documents originals.

7 Management of the data

The information on subjects of the study they will be maintained confidential And managed in basic at laws in force and regulations. The data collection system for this study uses security features built-in for all data to be transmitted in both directions, preventing non-access authorized at information on participants. Access to the system will be checked from a sequence Of codes Of identification And password assigned to users, returns available Alone to the personal authorized who have completed the necessary training. Before starting the study, and at each meeting, the staff will review the protocol and CRFs. During the study, you will need to periodically check the completeness from the folders clinics of the patients, the accuracy registrations to the CRF, membership to the protocol to Good Clinical Practice and the advancement of patient enrollment. The experimenter must maintain original documents for each patient in the study including hospital medical records containing demographic and medical data, laboratory data, electrocardiograms and the results of any other test or assessment. All information recorded on CRFs must be traceable to original documents in the patient file. Staff must also keep the consent form informed signed in original (a copy signed he comes released to the patient)

Documento Studio WOUND-H Valutazione prestazioni e sicurezza [acido ialuronico lineare per il trattamento delle ferite]	Codice NA-01-23		
v. 2 del 26 giugno, 2023			

8 Risks For the patients

Not I am States identified details risks tied to the treatment topical with acid hyaluronic linear in wounds post-surgical.

9 Management of the events adverse

9.1 Events adverse

The events adverse due to use Of acid hyaluronic In the treatment from the wounds I am generally traceable to phenomena Of intolerance to the product And solvable in few days without treatment.

Everyone The events adverse insurgents during The treatment, right away After The treatment And In the period Of follow up will be recorded in the “Adverse Event Form” (Annex I of the CRF). Adverse events will come classified by severity, relationship with the device being studied, intended or not, need Of treatment.

9.2 Definition Of event adverse (AE) and effect adverse of the device (HADES)

A AE / HADES And any change adverse respect at the condition basal of the subject, it's worth it to to say any unfavorable and unintended sign including an abnormal laboratory result, symptom or illness That And considered clinically relevant For The doctor That Yes verify In the course from the testing, regardless of whether it is considered device-related or not doctor.

The AE /HADES include:

- Exacerbation Of a illness pre-existing.
- Increase from the frequency or of intensity Of a illness episodic pre-existing or Of a condition medical.
- Illness or condition medical detected or diagnosed After The treatment with The device doctor,Also self could be to be was present Before of the beginning of the investigation clinic.
- Illness persistent continues or symptoms present to the basal That they get worse After the beginning of the investigation clinic.
- Lack Of effectiveness In the treatment acute Of a illness dangerous For there life.
- Events considered give it experimenter as related to procedures of the investigation clinic.
- Abnormal assessments, such as ECG and physical examination findings, should be reported as events adverse / HADES self they represent a result clinically significant That Not era present to the basal or worsened over the course of the investigation clinic.
- The anomalies of the test Of laboratory they must to be reported as AE/ADE self they represent a find clinically significant, symptomatic or less, That Not era present to the basal or got worse In the course

Documento Studio WOUND-H Valutazione prestazioni e sicurezza [acido ialuronico lineare per il trattamento delle ferite]	Codice NA-01-23	v. 2 del 26 giugno, 2023	 NOVA ARGENTIA
--	---------------------------	--------------------------	---

of the investigation clinic has carried to the interruption or at the Suspension of the treatment with The devicedoctor.

The AE/ADE Not include:

- The interventions planned or The occur Of endpoint specified In the CIP Not I am considered AE/ADE, self not otherwise defined.
- Medical or surgical procedure, for example surgery, endoscopy, tooth extraction, transfusion. However, the event leading to the procedure is an AE. If this event is serious, the procedure must be described in the storytelling SAE/SADE.
- Illness pre-existing or condition medical That Not it gets worse.
- Situations in which Not Yes And verified a change adverse, to example hospitalizations For surgery aestheticselective or for reasons social and / you hate convenience.
- Improper use of medical devices or concomitant medications without signs or symptoms. However, the use improper needs to to be mentioned In the register Of inventory of the devices doctors/card Of treatment.

Events adverse serious (SAE)/Effects adverse serious of the devices (SADE)

A event adverse serious (SAE)/effect adverse serious of the device (SADE) And defined as anyAE/ADE That satisfy at least one of the following criteria:

- bring to death,
- brings to a serious deterioration from the Health of the subject That
 - 1) has caused a illness or a wound dangerous For there life,
 - 2) has behaved a compromise permanent Of a structure corporeal or Of a function bodily,
 - 3) has behaved The recovery hospital or The extension of the recovery in course,
 - 4) has behaved a intervention doctor or surgical For to prevent a compromise permanentfrom the structure corporeal you hate a function corporeal.
- leads suffering fetal, death fetal or anomaly congenital or defect congenital.
- And a event doctor important That could be Not provoke immediately there death, to be dangerous For there life or request The recovery in hospital, but can to be considered as SAE / SADE when, based on appropriate medical judgment, it may compromise the subject and may require a intervention doctor or surgical For to prevent one of the outcomes listed in definitions Of which above.
- show the onset Of a cancer malignant.

The danger Of life Yes reports to a event in which The subject era to risk Of death to the moment of the event. Not Yes reports to a event That hypothetically it would have could to cause there death self is state more serious

All adverse events that occurred during treatment, immediately after treatment and in the follow-up period up will be recorded in the “Adverse Event Form” (Annex I of the CRF). Adverse events will come classified by severity, relationship with the device being studied, intended or not, need Of treatment.

Documento Studio WOUND-H Valutazione prestazioni e sicurezza [acido ialuronico lineare per il trattamento delle ferite]	Codice NA-01-23	v. 2 del 26 giugno, 2023	 NOVA ARGENTIA
--	---------------------------	--------------------------	---

9.3 Hospitalization – Extension of the recovery existing

Hospitalization is defined as an overnight stay in a hospital unit and/or emergency room.

A overnight stay additional defines a extension of the recovery existing.

How much follows Not And considered a SAE/SADE And needs to to be reported Alone as AE/ADE:

- Treatment in case Of emergency or For a event That Not satisfies there definition Of severity Of whichabove And does not entail hospital admission.

THE following reasons For the hospitalizations Not I am considered events adverse And Therefore Not SAE:

- Hospitalizations For surgery aesthetics elective, reasons social and/or Of convenience.
- Monitoring standard Of a illness pre-existing or condition medical That Not And worsened, to example, hospitalization For angiography coronary in a subject with angina pectoris stable.
- Treatment elective Of a illness pre-existing or condition medical That Not And worsened, to example, hospitalization For chemotherapy For cancer, replacement elective of the hip For arthritis.

9.4 SAE/SADE relative at procedures mandatory of the study

Such SAE/SADE are defined as SAE/SADE that appear to have a reasonable possibility of relation causal (valid to to say, a relation Not can to be excluded) with the procedures mandatory of the study (excluded there administration Of devices doctors) as the interruption of the previous treatment of the subject or the complication of a mandatory invasive procedure (for example, blood sampling, cardiac catheterization) or car accident on the way to the hospital for a visit Of study, etc.

